## 9/108

10/108

#### **1 INFORMATION TAKEN FROM THE PROTOCOL**

# **1.1 Study Objectives**

# 1.1.1 Primary Objective

The primary study objective is to assess the efficacy of two doses of Dysport (8 Units/Kilogram (U/kg) and 16 U/kg) compared to Dysport 2 U/kg used in the treatment of upper limb spasticity in children with cerebral palsy (CP) following a single treatment.

# 1.1.2 Secondary Objectives

The secondary study objective is to assess the long term safety of multiple treatments of Dysport used in this study population.

# 1.1.3 Tertiary Objectives

The tertiary study objectives CCI

quality of life (QoL) CCI

## 1.2 Study Design

This is a phase III, multicentre, double blind, prospective, randomised, controlled multiple treatment study. Subjects will receive a maximum of four treatments over the course of a minimum of one year's study participation.

At study entry, subjects will be randomised into one of the following three treatment groups for Treatment Cycle 1:

- Group A: Dysport 16 U/kg in one upper extremity (the study limb).
- Group B: Dysport 8 U/kg in the study limb.
- Group C: Dysport 2 U/kg in the study limb.

Randomisation will be in a 1:1:1 ratio. Stratification will be performed according to age range (2 to 9 years and 10 to 17 years) and BTX (Botulinum Toxin) naïve or non-naïve status assessed at baseline.

For Treatment Cycles 2, 3 and 4, subjects are planned to receive Dysport 8 U/kg or 16 U/kg according to the treatment allocation by the IRS and will remain double blind throughout the study. However, it is possible that subjects will not receive the planned treatment as dose adaptations (reduction or increase) will be possible based upon the Investigator's judgements regarding safety and efficacy. The total dose for the study limb must not exceed 320 U in the 8 U/kg group and 640 U in the 16 U/kg group.

The planned retreatment interval is 16 weeks and a maximum of four treatments will be administered.

At study entry, a primary targeted muscle group (PTMG), either the elbow flexors or wrist flexors, will be nominated by the Investigator. The PTMG can be changed for subsequent treatments, from elbow to wrist flexors or wrist to elbow flexors, provided that the following criteria are fulfilled:

- The Modified Ashworth Scale (MAS) score of the other muscle group not selected for the last treatment (new PTMG) must be higher than the last treatment PTMG, and
- The new PTMG must have a modified MAS score of greater or equal to 1+.

For Treatment Cycles 2, 3 and 4, injection into the lower extremity/extremities and the nonstudy upper limb will be allowed at the same time as the study limb is injected.

The stages of the study and the planned doses for the study are provided in Figure 1.

Figure 1 Planned Study Structure and Dose Modifications Available During the Study

#### Injection

All treatments

After each treatment administration, the follow up visit schedule is as follows:

- Week 2 (telephone call, safety follow up).
- Week 4 (telephone call, safety follow up).
- Week 6.
- Week 12 (telephone call, safety follow up).
- Week 16.

At Week 16, subjects will be assessed for their eligibility to receive the next treatment. Subjects who are eligible for retreatment will be given the next treatment. Any subjects not eligible for retreatment will be evaluated every 6 weeks  $\pm 2$  weeks in additional visits until they are eligible for retreatment.

Each subject will participate in the study for approximately 1 year to 1 year and 9 months depending on the number of treatments administered and the treatment intervals. The duration of the follow up period will be dependent upon the treatment interval as follows:

• All subjects whose first three treatment intervals fall between  $\ge 16$  and  $\le 22$  weeks will receive four treatments and will exit the study as soon as a new

injection is required and no later than 22 weeks after last injection (up to a maximum of 1 year and 9 months' study duration).

• All other subjects will not be given any further study treatment after Week 52 and will exit the study after 16 weeks of follow up of the last treatment.

#### 1.2.1 Study Treatment

Subjects will receive a fixed dose of Dysport 2 U/kg, 8 U/kg or 16 U/kg in the study upper limb in Treatment Cycle 1 and are planned to receive Dysport 8 U/kg or 16 U/kg in subsequent treatments according to the treatment allocation by the IRS, illustrated below, and both Investigators and subjects will remain blinded throughout the study. The allocated dose will be reconstituted to a fixed volume of 1.6 mL for injection.

| Group            | Number of | Treatment              | Treatment Cycles                 |
|------------------|-----------|------------------------|----------------------------------|
|                  | Subjects  | Cycle 1 (a) | 2, 3 and 4 (a) |
| А                | 70        | Dysport 16 U/kg        | Dysport 16 U/kg                  |
| В                | 70        | Dysport 8 U/kg         | Dysport 8 U/kg                   |
| C (b) | 70        | Dysport 2 U/kg         | Dysport 8 U/kg or                |
|                  |           |                        | Dysport 16 U/kg                  |

 Table 1
 Planned Dysport Dose per Group and Treatment Cycle

 $^{(a)}$  The total dose for the study limb must not exceed 320 U in the 8 U/kg group and 640 U in the 16 U/kg group.

(b) In this group, dynamic dose dispensing will be done by IRS at Treatment Cycle 2 to maintain a balance between subjects receiving 8 U/kg and 16 U/kg.

For Treatment Cycles 2, 3 and 4, and according to subject response, if any given total dose is not tolerated, the Investigator will request a dose reduction of 50% in the IRS. CC

For Treatment Cycles 3 and 4, if any given total dose is not adequate for the treatment of the subject's upper limb spasticity, the Investigator can request a dose increase in the IRS.

dose increase is possible for those subjects who were given Dysport 16 U/kg as the subject was already given the highest dose allowed in the study. CCI

No

CCI

. If there is no need to inject the lower limbs, and only the non-study upper limb is to be injected (on top of the study upper limb), the dose in the non-study upper limb should not exceed the dose detailed in Table 3.

 Table 3
 Dysport Dose in the Non-Study Upper Limb at Treatment Cycles 2, 3, and 4

| Body Weight (kg) | Maximum Dose                   |
|------------------|--------------------------------|
| 10 to 40         | 5 U/kg, calculated up to 40 kg |
| 40 and over      | 200 U                          |

If there is no need to inject the non-study upper limb and only one or two lower limb(s) are to be injected (on top of the study upper limb), the dose in the lower limb(s) should not exceed the dose detailed in Table 4.

 Table 4
 Dysport Dose in the Lower Limb(s) at Treatment Cycles 2, 3, and 4

| Body Weight (kg) | Maximum Dose                    |
|------------------|---------------------------------|
| 10 to 36         | 10 U/kg, calculated up to 36 kg |
| 36 and over      | 360 U                           |

## 1.2.2 Study Population

Approximately 210 male and female subjects will be randomised into the study. Subjects will be between 2 and 17 years of age, with a body weight of  $\geq 10$  kg, with a diagnosis of CP and who have increased muscle tone/spasticity in at least one upper limb. Additionally, subjects must have a MAS score  $\geq 2$  in the upper limb PTMG of the study limb (the limb to be injected at Treatment Cycle 1) at the baseline visit and be classified as Gross Motor Function Classification System (GMFCS) Level 1 to 4.

|  | Subjects must also |
|--|--------------------|
| not have any fixed myocontracture in the upper limb PTMG | of the study limb, |
| CCI  |                    |
|  | known              |
| sensitivity to BTX treatment, CCI                        |                    |
|  |                    |
|  |                    |
|  |                    |

# 1.2.3 Study Exposure

The overall duration of the study is anticipated to be approximately 4 years and 9 months. Individual subject participation will be approximately 1 year to 1 year and 9 months, depending on the number of treatments administered and the treatment intervals. The 1 year and 9 month follow up period will enable subjects whose first three treatment intervals fall between >16 and  $\leq$ 22 weeks to receive four treatments, therefore providing efficacy data for a minimum of 1 year.

15/108

## **1.3** Methods and Procedures

## 1.3.1 Subject Identification and Allocation to Study Treatment

All subjects enrolled must be identifiable throughout the study. The Investigator will maintain a list of subject numbers and names to enable records to be found at a later date if required.

At screening, potential subjects will be allocated a subject number. Following confirmation of eligibility for the study, subjects will be given a randomisation number and allocated to one of the treatment groups specified in Section 1.2.

## 1.3.2 Subject Assessments

## 1.3.2.1 Efficacy Assessments

MAS: A six-point scale which measures the amount of muscle tone by measuring the resistance of the muscle to passive lengthening or stretching [4]. The Investigator will grade muscle tone in the PTMG (elbow flexors or wrist flexors) from 0 (no increase in tone) to 4 (affected part(s) rigid in flexion or extension). The MAS will also be used to assess muscle tone in the injected muscles (elbow, wrist and finger flexors) in the study limb other than the ones of the PTMG, as well as to assess muscle tone in the injected muscles of the nonstudy upper limb.

The MAS will be obtained at baseline, at Week 6 and Week 16 of each Treatment Cycle, and also at the end of study (EOS) visit or early withdrawal (EW).

Also quantitative analyses on the MAS score will be performed, the original score '1+' will be considered as the derived numeric score '2' and the higher original numeric scores will be incremented by one as summarized in Section 3.2.13.19.

Physician's Global Assessment Scale of Treatment Response (PGA): The PGA of treatment response will be assessed by asking the Investigator the following question: 'how would you rate the response to treatment in the subject's upper limb since the start of the study?' Answers will be made on a nine-point rating scale (-4: markedly worse, -3: much worse, -2: worse, -1: slightly worse, 0: no change, +1: slightly improved, +2: improved, +3: much improved, and +4: markedly improved).

The PGA of treatment response will be obtained at baseline, at Week 6 and Week 16 of each Treatment Cycle, and also at the EOS/EW.

• Goal Attainment Scale (GAS): A functional scale used to measure progress towards individual therapy goals. At baseline of each Treatment Cycle one to three individual goals will be defined for each subject by the Investigator and the child's parents/guardians/caregivers prior to treatment. The importance and difficulty of each selected goal will be rated on a scale from 0 (Not at all important/difficult) to 3 (very important/difficult). Exactly one goal (the primary goal) must be rated as very important. Post-baseline the outcome to reach each goal will be rated on a 5-point scale (-2: Much less than expected outcome, -1: somewhat less than expected outcome, 0: expected outcome, 1: somewhat more than expected outcome, 2: Much more than expected outcome) has to be determined.

The GAS for each goal will be evaluated post-baseline at Week 6 and Week 16 of each Treatment Cycle, and also at the EOS/EW, and the total GAS score will be calculated using the formula in Section 3.2.13.20. A total GAS score of 50 means all individual goals have been achieved as expected.

Paediatric Quality of Life (PEDsQL) Inventory: Parents/guardians will be asked to complete questionnaires on their child's QoL [15] at each post-treatment visit to the study centre except Week 6. The PedsQL parent inventory measures healthcare concepts for children/adolescents of ages 2 to 18 years of age [16]. The Generic Core Scales cover four multidimensional scales including physical, emotional, social and school aspects with three

summary scales of total scale score, physical health summary score and psychosocial health summary score.

Parents/guardians will also complete the Condition-specific Module in CP (in countries where translation is available) [16], which is a complement to the Generic Core Scale of the PedsQL. It is designed to provide greater measurement sensitivity for circumscribed populations. The answers to the questionnaire will be obtained at baseline, at Week 16 of Treatment Cycle 1, and at the EOS/EW.

- For each defined scale a score is calculated using the transformations in Section 3.2.13.21.
- 1.3.2.2 Safety Assessments
  - Adverse Events (AEs): Collected from the signing of informed consent up until the EOS.
  - Physical examination: A physical examination will be carried out by a physician or by another qualified staff member designated by the Investigator at the screening visit and at the EOS/EW. If in the opinion of the Investigator there are any clinically significant changes in the physical examination findings (abnormalities) they will be recorded as AEs.
  - Vital signs: Systolic and diastolic blood pressure (BP), and heart rate (HR) will be measured at each visit to the study centre. Blood pressure will be measured with the subject in a sitting position.
  - Electrocardiogram (ECG): Subjects will have a set of three 12-lead ECG recordings taken at the screening visit (considered as baseline assessment), then subsequently one 12-lead ECG at Treatment Cycle 1, Week 6 and at the EOS/EW. The 12-lead ECG recordings will be performed at a paper speed of 25 mm/sec, recorded with the subject supine. Analysis of the ECG results will be performed in a central laboratory.

Analysis of the duration of the QT/QTc interval (for both Fridericia's and Bazett's methods), the HR and the presence of any of the following ECG abnormalities: new morphologies, arrhythmias, second degree AV block, third degree AV block, ST segment abnormalities, T-wave abnormalities, U-wave abnormalities, myocardial infarction, right bundle branch block, left bundle branch block will be performed. These and any other clinically relevant abnormality will also be reported by the central provider to the Investigator and recorded as an AE.

• Clinical laboratory parameters:

Clinical chemistry (including serum Alkaline Phosphatase (ALP) - total and bone isoenzyme, and HbA1c): Blood sample will be collected at Treatment Cycle 1, Day 1 (baseline) and EOS/EW. In addition, a blood sample for serum ALP - total and bone isoenzyme, and HbA1c only will be collected at Treatment Cycle 1, Week 16.

Pregnancy test: At Day 1 of each treatment for all female subjects of childbearing potential and for those subjects reaching Tanner Stage II or more breast development, a urine sample will be collected for a pregnancy test. If

the urine pregnancy test is found to be positive, it will be followed up with a serum pregnancy test (1 mL blood) conducted at the central laboratory.

• Presence of antibodies against BTX-A (BTX-A-Abs): Tests for the presence of BTX-A-Abs will be done prior to study treatment administration at baseline and at the EOS/EW.

# 1.3.2.3 Other Assessments

Other assessments collected include the following, recorded at screening only unless otherwise specified:

- Demographics (date of birth/age, sex, ethnicity and race)
- Medical and surgical history (including ongoing medical history)
- Cerebral Palsy history and status
- Botulinum toxin treatment history
- Gross motor function classification system level
- Neurological examination
- Body weight and height (recorded at baseline, Week 16, and at the EOS/EW)
- Tanner grading scale for breast development (all female subjects)
- Hypertonia assessment tool
- Manual Ability Classification System (MACS) for subjects older than 4 years of age (4 years included) and mini-MACS for subjects between 2 and 4 years of age (4 years excluded) (baseline only)
- Prior and concomitant medications and non drug therapies (including physiotherapy, and occupational therapy) and concomitant surgical procedures throughout the study
- Home exercises and use of splints and/or orthoses throughout the study.

# 1.3.2.4 Withdrawal/Discontinuation

Under no circumstances will subjects be randomised into this study more than once. If one or more of the following occurs, the subject will be withdrawn from the study:

- Withdrawal of informed consent
- Requirement for administration of concomitant medications and/or treatments that are not allowed under the study protocol
- Occurrence of an AE or other nonmedical event, that in the opinion of the Investigator, would not be in the subject's best interest were they to continue in the study
- Pregnancy
- Investigator's and/or Sponsor's decision to withdraw the subject if it is considered to be in the subject's best interest
- Continuous failure to comply with the provisions of the study protocol which is likely to have an adverse impact on the safety or wellbeing of the subject or subjects, or to jeopardise the scientific value of the study
- •

19/108

#### SAP Final Version 2.0: 19 Oct 2018

- Requirement during the study of an injection in the nonstudy upper limb or lower limb(s) without an injection in the study limb.

The exact reason(s) for withdrawal must be recorded, if available. If possible, a complete final examination should be performed for all subjects who withdraw. In case of withdrawal due to an AE, the subject should be followed up by the Investigator outside the study framework.

CONFIDENTIAL

#### SAP Final Version 2.0: 19 Oct 2018

# 1.3.4 Planned Sample Size

The sample size required for this study has been determined on the basis of the sample size estimate for each of the three criteria to be considered (superiority of any of the two tested Dysport doses to Dysport 2 U/kg on the primary efficacy endpoint, superiority of any of the two tested Dysport doses to Dysport 2 U/kg on the first secondary efficacy endpoint, and proper assessment of the long term safety of the two tested Dysport doses); the largest of these three estimates is used as the sample size of the study.

## Sample Size of the Study

Given the above sample size estimates, a targeted study sample size of 210 randomised subjects (i.e. 70 randomised subjects per treatment group) is considered sufficient to meet both the primary efficacy objective and the long term safety objectives.

Using a sample size of 210 as the largest of the three required figures means the actual power for the testing on the primary efficacy endpoint and the testing on the first secondary efficacy endpoint rises to 99% and 99%, respectively. As a result, the actual power of the study to detect a significant effect of any tested Dysport dose for both efficacy endpoints (US-targeted methodology) is 98% (= 99% x 99%).

# 2 SUBJECT POPULATIONS (ANALYSIS SETS)

## 2.1 Efficacy

#### 2.1.1 Modified Intent-to-treat Population

The modified Intent-to-treat (mITT) population will consist of all randomised subjects who received at least one injection of the study treatment and had a MAS score in the PTMG assessed both at baseline and at Treatment Cycle 1, Week 6. The mITT population will be analysed using the dose group as randomised, regardless of treatment actually received.

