# 2.1.2 Per Protocol Population

The Per Protocol (PP) population will consist of all subjects from the mITT population who are not major protocol violators between baseline and the Treatment Cycle 1, Week 6 visit (inclusive).

The allocation of subjects to the PP population will be finalized and documented prior to unblinding.

The PP population will be analysed using the dose group as randomised, regardless of treatment actually received.

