# 2.6 **Populations of Primary Interest**

For the fixed dose Treatment Cycle 1, the primary population for the efficacy analyses will be the mITT population.

Secondary populations of interest for the efficacy analyses will be the PP population and the Randomised Population.

For the evaluation of efficacy over repeated treatments, analyses per Treatment Cycle will be performed using the available data from all subjects of the mITT population in the specified treatment cycle according to the planned dose for the specified treatment cycle.

The safety analyses of the fixed dose Treatment Cycle 1 will be performed on the safety population.

For the evaluation of safety over repeated treatments, analyses per Treatment Cycle will be performed using the available data from all subjects of the safety population in the specified treatment cycle according to the actual dose received in the specified Treatment Cycle.

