# 3.2.2 Efficacy

All efficacy analyses for the fixed dose Treatment Cycle 1 will be performed on the mITT population. Assessment of repeat efficacy by Treatment Cycle will only include subjects who received the treatment in the designated Treatment Cycle. The primary and secondary efficacy analyses (designated efficacy parameters at Week 6 of the fixed dose Treatment Cycle 1) will also be performed on the PP population. Efficacy tables will be presented by treatment group of the Study Limb Dose, see Section 3.2.1.1.

Baseline will be defined as the last measurement collected prior to receiving the initial study treatment in Treatment Cycle 1 on Day 1. MAS score, CC

may also have been measured in muscle groups other than those injected. Only assessments from subjects who received treatment in the respective muscle group will be included in the analyses.

In addition to the analyses described below, descriptive statistics will be provided for all efficacy endpoints.

34/108

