3.2.2.7 Subgroup Efficacy Analyses and Covariates

Covariates used in models of efficacy analysis will be the same as those mentioned in sections 3.1.1 and 3.1.2.

The model will be run including the centre effect, which will be removed if the model does not converge.

The following additional subgroup analyses will be conducted on the MAS and the PGA of the mITT population:

Primary (MAS) and First Secondary (PGA) Efficacy Endpoint

- Age group (2 to 9 years and 10 to 17 years)
- BTX status at baseline (naïve or non-naïve)
- Sex (Male or Female).

MAS and PGA at Treatment Cycle 1 Week 16

• Physiotherapy/Occupational therapy status at Week 16 (No/Yes): Subjects without physiotherapy nor occupational therapy before week 16 of Treatment Cycle 1 versus subjects with physiotherapy and/or Occupational therapy between Baseline and Week 16 of Treatment Cycle 1.

Statistical analyses will include:

- A summary table of raw values and changes from baseline to all visits, by treatment group and overall, in each subgroup separately.
- A rank ANOVA model (score= subgroup\_indicator + treatment + BTX stratum + age group + interaction subgroup \* treatment + centre) or rank ANCOVA model (change = baseline + subgroup\_indicator + treatment + BTX stratum + age group + interaction subgroup \* treatment + centre).

Following contrast analyses for reporting will be performed in case the p-value from the interaction term is deemed statistically significant (lower than 0.1):

- i. The Least Square Mean (LSMeans) of change from baseline in each subgroup, for each treatment group separately, together with its 95% CI,
- ii. Difference in LSMeans in each subgroup between each active dose and Dysport 2 U/kg, together with its 95% CI and the p-value of the test  $H_0$ :Adjusted MeanDysport (8 and 16 U/kg) = Adjusted MeanDysport 2 U/kg.

The ANOVA or ANCOVA models will only be run if there are at least 20 subjects in at least one treatment group. 20 subjects was deemed to be a reasonable number of subjects in order for the analyses to be considered to be meaningful rather than being calculated using any formal statistical methodology.

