# 5 CHANGES FROM PROTOCOL

- 'Treatment Cycle' is used instead of 'Treatment'
- According to the protocol listings will be sorted by treatment group and subject ID. As the treatment group for a subject can change during the course of the study, listings will be presented by subject ID instead.
- MAS responder analyses in injected muscle group (elbow, wrist and finger flexors) has been added to the tertiary efficacy endpoints.
- GAS responder analyses has been added to the tertiary efficacy endpoints
  - CCI

66/108

- Time to retreatment. The time from injection to retreatment (in weeks) will be summarized by treatment group and overall in the mITT population for subjects retreated at any time from the Week 16 visit onwards. Subjects who are not retreated are censored at the date of their last recorded visit in the treatment cycle or observational phase. Results from the Kaplan-Meier analysis will be obtained using the SAS® LIFETEST procedure. A summary table will present the results from the Kaplan-Meier analysis and will include the numbers of subjects at risk, censored and with an event (retreated) for each time interval, as well as the Kaplan-Meier estimates, the median time to event, and 95% CI. In addition, the Kaplan-Meier estimated survival functions will be plotted. Summary tables for the number and percentages of subjects retreated at each Treatment Cycle from Week 16 onwards and the time to retratment will also be displayed. An individual data listing will present the actual time to retreatment for each subject.
- The sensitivity analysis on the primary and first secondary endpoint to assess the impact of missing values will be performed on the full population of all randomised subjects instead of the population of all randomised subjects who received at least one injection of study treatment.
- According to the study protocol the theoretical maximum dose for the study limb was 640 U in the 16 U/kg group, however, due to the reconstitution of Dysport the maximum actual dose is 650 U.

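### The mITT set is defined by one Cycle 1 Week 6 MAS score, yet it is also the analysis set for efficacy endpoints that do not need that score

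*SAP*

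**What the plan says.** SAP 2.1.1, following Protocol 11.2, limits the mITT set to randomised subjects with at least one injection who "had a MAS score in the PTMG assessed both at baseline and at Treatment Cycle 1, Week 6". Other sections then apply this set widely:

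- **Cycle 1 efficacy (SAP 3.2.2):** "All efficacy analyses for the fixed dose Treatment Cycle 1 will be performed on the mITT population". This covers both secondary endpoints, PGA and GAS at Week 6, and every Week 16 analysis.
- **Subgroups (SAP 3.2.2.7):** "The following additional subgroup analyses will be conducted on the MAS and the PGA of the mITT population". The list includes MAS and PGA at Week 16.
- **Repeat treatment (SAP 2.6):** "analyses per Treatment Cycle will be performed using the available data from all subjects of the mITT population in the specified treatment cycle".
- **Time to retreatment (SAP 5):** it "will be summarized by treatment group and overall in the mITT population for subjects retreated at any time from the Week 16 visit onwards", with a Kaplan-Meier analysis.
- **Per protocol (SAP 2.1.2):** this set "will consist of all subjects from the mITT population who are not major protocol violators", so it cannot bring back a child whom mITT has excluded.

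Two departures are visible, both at Cycle 1 Week 6 (SAP 3.2.2.2, 3.2.2.4 and 3.2.4.1). The primary endpoint has a sensitivity analysis on all randomised subjects, in which a missing Week 6 MAS is replaced by the baseline score. For US registration only, PGA has two sensitivity analyses on all randomised subjects, in which only missing PGA scores are imputed. SAP 2.6 names the Randomised Population as a secondary efficacy population, but the visible text uses it only for these analyses.

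**The concern.** The primary analysis needs a Week 6 MAS, so requiring one there is natural. No other endpoint needs it. GAS and PGA have their own scores, Week 16 and later MAS changes use the baseline and the later visit, and time to retreatment uses injection and visit dates.

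The exclusion can occur in two ways. A child may miss the Week 6 visit and then continue. Or a child may attend and have PGA and GAS scored but no MAS, which is possible because Protocol 8.1 requires different assessors for PGA and for muscle tone. No visible text makes a Week 6 MAS a condition for staying in the study or for retreatment (Protocol 4.1.3, 6.4 and 9.1.3.6), although some criteria there are redacted.

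At stake are observed efficacy data, and the population to which the GAS, Week 16, retreatment and repeat-cycle results refer. As written, they describe children who were MAS-scored at Week 6, not treated children.

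**Working it through.** **1. Endpoints against analysis sets**

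| Analysis | Set | Needs Cycle 1 Week 6 MAS? | Visible all-randomised analysis |
|---|---|---|---|
| MAS change, Week 6 | mITT | Yes | Yes |
| PGA, Week 6 | mITT | No | US registration only |
| GAS, Week 6 | mITT | No | None |
| MAS, PGA, GAS, Week 16 | mITT | No | None |
| Week 16 subgroups (MAS, PGA) | mITT | No | None |
| Time to retreatment | mITT | No | None |
| Efficacy, Cycles 2 to 4 | mITT, treated in that cycle | No | None |

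Only the first row needs the score that defines the set.

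**2. What a continuing child loses**

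SAP 1.3.2.1 schedules MAS, PGA and GAS at Week 6 and Week 16 of each cycle, so there are two such visits per cycle. A child who misses only Cycle 1 Week 6 and receives c cycles attends 2c − 1 of them: 1, 3, 5 or 7 for c = 1, 2, 3 or 4. All are left out of the mITT and PP analyses, as are the end-of-study assessment and time to retreatment. If the whole Week 6 visit is missed, no observed post-baseline efficacy value from that child reaches any visible efficacy analysis. The sensitivity analyses then use only the baseline MAS and imputed values.

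**3. How many children**

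The documents give no missing rate. Let m be the share without a Week 6 MAS and r the share of those who continue with later data. Both are unknown. The number losing later data is 210 × m × r, and r = 1 gives its ceiling:

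- m = 2%: 210 × 0.02 = 4.2
- m = 5%: 210 × 0.05 = 10.5
- m = 10%: 210 × 0.10 = 21
- m = 20%: 210 × 0.20 = 42

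With r anywhere from 0 to 1, the count for later endpoints runs from 0 to these ceilings.

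**4. Power**

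The stated figures in SAP 1.3.4 agree with each other: 3 × 70 = 210 and 0.99 × 0.99 = 0.9801, given as 98%. The two 99% figures cannot be reproduced, because the effect size, standard deviation and multiplicity text are not public.

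As a yardstick, assume a comparison of two means, two-sided 0.05, normal approximation, with 99% power at 70 per arm. The implied standardised effect is

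d = (1.960 + 2.326) × √(2/70) = 0.72.

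With n = 70 × (1 − m) per arm, power = Φ(d√(n/2) − 1.960):

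| m | n per arm | Power |
|---|---|---|
| 2% | 68.6 | 98.9% |
| 5% | 66.5 | 98.7% |
| 10% | 63.0 | 98.2% |
| 20% | 56.0 | 97.0% |

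For a weaker endpoint, say d = 0.5 (assumed), power falls from 84.1% to 80.1% at m = 10%. These are upper limits on the loss, since they treat every excluded child as having the endpoint observed. For the primary endpoint itself, the rule discards no Week 6 MAS value, because that value is absent in any case.

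**The case against.** A reader might infer that one missed visit deletes a child's whole efficacy record. The documents do not support that. The child stays in the all-randomised sensitivity analysis of Week 6 MAS and, for the US, in the two Week 6 PGA analyses, which explicitly extend to children outside mITT and keep an observed PGA. The by-subject listings (SAP 3.2) and the safety set (SAP 2.2) are also unaffected.

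Several other objections have force:

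- **Early withdrawals.** SAP 3.2.4.1 describes missing Week 6 values as arising from withdrawal before that visit. Week 6 is the first clinic visit after injection, since Weeks 2 and 4 are telephone contacts. A child who leaves before it has no later efficacy data to discard. This stands, and it is why the ceilings above cannot be read as children losing data.
- **Week 6 PGA and GAS.** A child who misses the visit has neither score. Observed Week 6 values are lost only when the child attends without a MAS. This stands.
- **Cycles 2 to 4.** These are descriptive (SAP 3.1.6), grouped by the planned dose of the cycle, and limited to children treated in it. They are already selected on post-randomisation events. This lowers the stakes, but it does not justify a further filter with no bearing on the cycle reported.
- **The remedy also selects.** An observed-case set for each endpoint still depends on attendance. That is true, but it depends on having the endpoint being analysed, and it keeps data that the current rule discards.
- **Hidden text.** SAP 3.1.5, some tertiary endpoints and the table index are not public, so a wider population stated there cannot be excluded.

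**Conclusion.** The concern holds in this form. A rule built for the primary endpoint governs Week 6 PGA and GAS, Week 16, the subgroup analyses, time to retreatment and Cycles 2 to 4. In the visible text, GAS, Week 16, time to retreatment and Cycles 2 to 4 have no analysis on a wider set. For a child who continues without the Week 6 MAS, up to seven attended Week 6 and Week 16 visits are left out.

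The number of such children is unknown and may be small. The effect on power is slight under the assumptions above, so this is not a power problem. It is a needless loss of valid data and a selection on an unrelated post-randomisation condition. The conclusion rests on the public text only. It is a worthwhile, cheap improvement and does not threaten the primary analysis.

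**What to change.** Keep mITT for the primary endpoint, and change the set elsewhere:

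- **Every other Cycle 1 endpoint:** all randomised and treated subjects, by randomised dose, who have that endpoint (and its baseline where the model needs one) at the visit analysed.
- **Cycles 2 to 4:** all subjects treated in that cycle.
- **Time to retreatment:** all treated subjects.

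Amend SAP 2.6, 3.2.2, 3.2.2.7 and the time-to-retreatment entry in section 5. Record the departure from Protocol 11.2 and 11.2.1 in SAP section 5. Because MAS and PGA are linked in the US joint power statement, check that SAP 3.1.5 is worded consistently with the new sets.

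The cost is one more population flag, revised wording and slightly different n between endpoint tables. The planned sample size and stated power figures do not change.
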